11.5 Surgical proficiency vaginal cerclage

- Stich-operators
 - Each site appoints one or two local stich-operators for the study (both vaginal cerclage sites and laparoscopy-sites).
- Stich-site
 - The stich-site may be the laparoscopy-site or at the patient's local hospital.
 - \circ 1-2 stich-operators per stich-site depending on the number procedures.
- Stich-operators
 - Methods and Training
 - Suture "as high as possible" [19]
 - Pass the needle through collum substance and mucosa four to eight times
 - Must include enough tissue to withstand the strain of pregnancy
 - Avoid penetration of the cervical canal.
 - The stich at the posterior of the cervix is critical. Ensure, that it is applied as high as the stich at the anterior part of the cervix.
 - Tight the suture relatively much to ensure only a narrow cervical canal.

- Extra suture is applied if it can be placed higher up (surgeons discretion).
- USS verification of the cervical length at the 20 week's scan for quality assurance
 - Module: NORACT offers a PROMPT Flex Cervical Cerclage Module (scandidact.dk) training when appropriate.
- Voluntary feedback: The stich-operator may send a PROMPT Flex-cervix with a cerclage to [name] for evaluation and feedback.
- Supervision: In case of appointing new stich-operators, a local stich-operator supervises the first 3-5 procedures

12. Outcomes

All outcomes listed below are found in the electronic medical records of the participant and her child. The data is only accessed after verbal and written consent is given. Data from the children's medical records are passed on to the researchers.

Primary clinical outcome of the full trial

There are two prioritized outcomes based on a conditional hierarchical approach in the following order:

- 1. Delivery <32+0 weeks of gestation (definition: In the first subsequent viable pregnancy (ultrasound detected heart beat) beyond 14+0 weeks of gestation).
- 2. Baby death (defined as loss of a viable pregnancy beyond 14+0 weeks of gestation, stillbirth, late miscarriage or death of a live born infant within 28 days from date of birth or miscarriage).

Secondary clinical outcomes of the full trial

Maternal outcomes

- Maternal mortality surgery related.
 - Definition: All deaths of a female within 30 days of the cerclage procedure.
 - Time frame: 30 days after intervention/control
- Maternal mortality
 - Definition: All death of a female of any cause.

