Women who decline participation in the trial are asked to sign a separate consent form agreeing to share data on their birthdate, body mass index (BMI), obstetric history (i.e. number, delivery mode, interventions, and gestational age with previous deliveries), previous conization, current clinical findings (cervical length by inspection and ultrasound), their stated reason for declining participating in the trial, and their delivery outcomes. This information is collected for the purpose of assessing the internal validity and the generalizability of the trial and in order to estimate the feasibility of the interventions in eligible women. Second, this data will be presented in the final publication of the results.

15. Sample size

The primary outcome is delivery before 32+0 weeks of gestation. The sample size is based on a target difference of 15% (20% in the vaginal cerclage groups vs. 5% in the abdominal cerclage group). This effect size was estimated based on the rate of delivery before 32+0 weeks of gestation (33% in the vaginal cerclage group vs. 8% in the abdominal cerclage group) in data from Shennan et al.[6]. Since the women included in NORACT are likely to have a somewhat lower risk of PTB compared to the aforementioned study, we assumed a baseline event rate of 20% with the vaginal cerclage and 5% with laparoscopic cerclage (alpha 0.05 and power of 80%). This magnitude of target difference was determined to be important as well as realistic. We inflated for 10% attrition (for those who do not become pregnant, or have an early miscarriage) and a further 10% loss to follow up resulting in a total of 188 women (94 in each group).

For the outcome baby death, the proportions from Shennan et al.[6] were 21% in the vaginal cerclage group versus 3% with laparoscopic cerclage [6]. Again, taking into account the less high risk population in our study and with the sample size of 188 participants, we'd have a power of 80 to detect a target difference of 15%.

Given the uncertainty of the event rate in this less high risk population, it was agreed that the Independent Data and Monitoring Committee (IDMC) would monitor the pooled event rate throughout the study to assess the need to prolong the recruitment period and thereby increase the sample size.

16. Allocation

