Eligible women will be identified by the obstetrician during a pre-pregnancy consult. Women will be randomized by a local investigator using an online 24/7 available randomisation software imbedded to REDCap. The women will be randomised in a 1:1 ratio to either laparoscopic or vaginal cerclage with

stratification according to country. The randomisation programme will automatically transfer the entry data to the eCRF in REDCap.

17. Blinding

The trial is open-label.

18. Data collection

All data collection of clinical variables follows the informed consent from the participants. Data will be collected on electronic standardized forms (eCFR) on which almost every response is precoded. The forms are generated using REDCap.

If participants discontinue or their care deviate from the intervention protocols, we will continue to collect data, unless the woman specifically state that we cannot collect or store her data. The responsible investigator or an assigned and educated research staff member from the local clinical team will be responsible for data collection and entry. During the screening process, data* necessary to decide if the patient is eligible for the trial will be entered into REDCap. If the patient decline to participate and do not wish to sign the consent form for decliners or is not found eligible, all registered data will be deleted. The data collected during the screening process, is data that would be obtained for clinical reasons despite this trial and is relevant for the patient's treatment plan outside the trial. All further data will be obtained from the in-hospital electronic medical record after written consent is given. Data from the children's records will be shared within the project.

*The following data will be accessed from the in-hospital electronic medical record aiming to clarify if the potential participant meets the inclusion and exclusion criteria:

- Unique patient identifier (Danish Central Personal Register number)
- Patient name
- Length of cervix
- Body mass index
- Smoking (yes/no)
- Information on:
 - o Parity
 - Prior caesarean delivery
 - Cervical surgery (conizations)
 - o Previous preterm birth
 - Previous late miscarriages

Variables

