Data will be handled according to national laws on data protection (in Denmark including the General Data Protection Regulation and the Data Protection Act). In Denmark, the project is registered with the Central Denmark Region's internal list of research projects. Data will be used for the purpose outlined in this trial protocol.

20. Adherence

We have defined adherence as those participants in the vaginal cerclage group who receives a vaginal cerclage before 16+0 weeks of pregnancy and those participants in the laparoscopic cerclage group who receives a laparoscopic cerclage before 10+0 weeks of pregnancy. Subsequent exam-indicated vaginal cerclage in either group will count as adherent.

21. Analyses

All estimates of differences between groups will be presented with two-sided 95% confidence intervals, unless otherwise stated. For the primary outcome of preterm birth, a p-value will be produced, with statistical significance considered at the 5% level.

For the second prioritized primary outcome of baby death, we will incorporate a conditional hierarchical approach to hypothesis testing to ensure we appropriately control for the overall rate of type I error(5). If the primary outcome of preterm birth meets a superiority conclusion in favour of either a vaginal or laparoscopic cerclage, we will then proceed to examine any differences between the two procedures for baby death. If the p-value from this test (baby death) is less than or equal to 0.05 in the model (or if the 95% confidence interval does not contain one) we will declare superiority for this outcome.

Other secondary outcomes will be considered as exploratory; no adjustment for multiple comparisons will be made and hence significance should not be inferred from the confidence interval width.

All primary analyses (primary and secondary outcomes) will be conducted on a modified intention-totreat basis only including patients who are pregnant at time of randomisation or become pregnant

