after randomisation and carry a pregnancy beyond 14+0 weeks. Participants who have an early miscarriage will be excluded post randomisation, unless they have a viable pregnancy beyond 14+0 weeks later in the study period. The rationale behind this decision is, that an early miscarriage is unlikely to be caused by an incompetent cervix. Participants will be analysed in the intervention group to which they were randomised, and all participants shall be included whether or not they received the allocated intervention.

A secondary per protocol and as-treated analysis will be performed for each treatment group for the primary outcomes only (see section 20 for description of whom will perform the per protocol analysis).

Presentation of the quantitative data from the internal pilot will largely consist of descriptive statistics and comparisons between the two groups. The inclusion number will be described according to country, site, and groups in Table 1. The reasons for ineligibility, refusal, loss to follow-up, or missing data will be categorised and described as overall frequencies per country, site, and according to groups in Table 1. No outcome data will be available for evaluation.

Subgroup analyses will be conducted to determine whether there are signs of an effect for each prespecified subgroups. To ensure validity to the subgroup analysis, the factors considered for subgroup analyses is pre-specified below:

- Participants with a history of emergency/laboring caesarean section followed by a spontaneous singleton late miscarriage or preterm birth 14+0-28+0 weeks.
- Participants with a prior elective vaginal cerclage placement but nonetheless a spontaneous late miscarriage or PTB between 14+0 and 28+0* weeks
- History of a prior emergency cerclage with delivery between 14+0 and 28+0* weeks
- Participants with a history of one or more deliveries between gestational age 16+0 to 28 +0 and a clinical diagnosis of cervical insufficiency.
- Any conization and a short pre-pregnancy cervix (e.g. short ectocervix with inspection or below 15-20 mm with ultrasound)
- History of three or more deliveries GA 16+0 to 36+6 weeks

The statistical analyses and reporting will adhere to the Consolidated Standards of Reporting Trials (CONSORT)-guidelines[23, 24].

STATA and 'R' will be used for data management and analyses.

Patient inclusion and exclusion will be illustrated in a modified CONSORT flow diagram for non-pharmacologic trials[25] (see figure 1).

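### The section 20 adherence rule drops vaginal-arm losses between 14+0 and 16+0 that precede a still-permitted stitch from the per-protocol set, which can only lower that arm's event rate

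*Protocol*

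**What the plan says.** Four parts of the protocol bear on this.

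- **Outcomes (section 12).** The first prioritised outcome, delivery before 32+0, is assessed thus: "In the first subsequent viable pregnancy (ultrasound detected heart beat) beyond 14+0 weeks of gestation". The second, baby death, includes loss of a viable pregnancy after 14+0. Section 12 also defines late miscarriage as a delivery between 14+0 and 21+6, so a loss at 14 or 15 weeks is an event for both outcomes.
- **Timing of the vaginal stitch (section 11.2).** It may be placed at any time from detection of fetal heart activity to 16+0, and the clinician may wait for the nuchal scan result.
- **Adherence (section 20).** The adherent women in the vaginal arm are "those participants in the vaginal cerclage group who receives a vaginal cerclage before 16+0 weeks of pregnancy". In the laparoscopic arm the cerclage must be received before 10+0. A later exam-indicated vaginal stitch does not count against adherence in either arm.
- **Analyses (section 21).** "A secondary per protocol and as-treated analysis will be performed for each treatment group for the primary outcomes only". Section 20 is cited there for the per-protocol set only. The main analysis is a modified intention-to-treat analysis of women who carry a pregnancy beyond 14+0, grouped as randomised whatever they received.

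**The concern.** In the vaginal arm, adherence can be decided up to two weeks after outcome counting has begun. A woman must stay pregnant until her stitch to be classed as adherent, so the per-protocol vaginal group is selected partly on not yet having had the event. This is immortal time. In the laparoscopic arm adherence is settled at least four weeks before 14+0, and no such selection occurs.

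The woman affected has not departed from the protocol: the stitch was still permitted when she lost the pregnancy. Table 1 lists women with earlier losses or births from 14+0 onwards, and section 21 leaves out earlier miscarriages as unlikely to be cervical. A loss soon after 14+0 is thus the kind of event the trial is meant to count.

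At stake is the per-protocol estimate for the primary outcomes. Part of any gap between it and the main result could come from the definition of the set rather than from adherence.

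**Working it through.** **1. The plan's own sample size.** Inputs from section 15: 20% vaginal, 5% laparoscopic, alpha 0.05, power 80%. Section 16 gives 1:1 allocation, and section 21 implies a two-sided test ("All estimates of differences between groups will be presented with two-sided 95% confidence intervals"). With pooled variance and no continuity correction, the mean rate is 0.125 and

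n = [1.96 × √(2 × 0.125 × 0.875) + 0.842 × √(0.20 × 0.80 + 0.05 × 0.95)]² / 0.15² ≈ 75.1, so 76 per arm.

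The two 10% inflations give 76 / 0.9 / 0.9 = 93.8, so 94 per arm and 188 in total, as stated. The analysable number is therefore 76 per arm, with 0.20 × 76 = 15.2 expected events in the vaginal arm.

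**2. Same loss, two arms.** Take a loss at 15 weeks.

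| | Vaginal arm, not yet stitched | Laparoscopic arm, cerclage before 10+0 |
|---|---|---|
| Event for both prioritised outcomes | yes | yes |
| In the modified intention-to-treat analysis | yes | yes |
| Adherent under section 20 | no | yes |
| In the per-protocol set | no, event removed | yes, event kept |

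The sentence on later exam-indicated stitches does not help, because it needs a pregnancy that is still ongoing.

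**3. Size.** Let p be the true vaginal-arm rate, u the share of the arm unstitched at 14+0, and h their risk of losing the pregnancy between 14+0 and the stitch. Every woman removed has an event, so

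per-protocol vaginal rate = (p − uh) / (1 − uh).

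This is below p whenever uh > 0 and p < 1. The path leaves the laparoscopic rate alone. The protocol gives neither u nor h, so both are assumed here. With p = 0.20 and 76 women:

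| u | h | uh | Women removed | Per-protocol vaginal rate |
|---|---|---|---|---|
| 0 | any | 0 | 0 | 20.0% |
| 0.25 | 1% | 0.0025 | 0.2 | 0.1975/0.9975 = 19.8% |
| 0.50 | 2% | 0.0100 | 0.8 | 0.1900/0.9900 = 19.2% |
| 0.75 | 3% | 0.0225 | 1.7 | 0.1775/0.9775 = 18.2% |
| 1 (extreme) | 5% | 0.0500 | 3.8 | 0.1500/0.9500 = 15.8% |

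Over the middle three rows the laparoscopic-to-vaginal risk ratio moves from 0.05/0.20 = 0.25 to between 0.253 and 0.275. If the true rate were 20% in both arms, it would move from 1.00 to between 1.01 and 1.10. In the extreme row the two ratios are 0.317 and 1.27.

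For baby death the same women leave the set. Section 15 gives a target difference for that outcome but no assumed rates for this population, so no separate figure is calculated.

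**The case against.** **The effect is small and the main result is safe.** This stands. Women stitched before 14+0 contribute nothing, and the others contribute two weeks at most. The hierarchical test does not use the per-protocol set. A reader might infer that the trial's main conclusion is biased; section 21 rules that out by keeping these women in the modified intention-to-treat analysis.

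**A larger figure is tempting.** If 2% or 4% of the whole vaginal arm were lost in this window before a stitch, the rate would fall to 0.18/0.98 = 18.4% or 0.16/0.96 = 16.7%. Nothing in the protocol supports those inputs. At 4%, one fifth of all vaginal-arm events before 32+0 (4 of 20 points) would fall within two weeks, and only among women not yet stitched.

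**Section 20 also removes laparoscopic-arm women.** A woman who passes 10+0 without the procedure leaves the per-protocol set with any later event, and section 11.1 foresees unplanned pregnancy after randomisation. This stands too. The path described here has a known direction, but the net bias of the per-protocol comparison is not established, and a reader should not infer that events leave one arm only.

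**The as-treated analysis.** A reader might infer that the adherence rule biases this analysis as well. Section 21 cites section 20 for the per-protocol set alone, and the protocol does not define the as-treated groups. Its SAP was not available here and may do so. The same issue arises only if women are grouped by cerclage received.

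**Per-protocol should mean treated.** One could say that a woman without a stitch does not belong in a per-protocol vaginal group. But the vaginal strategy in section 11.2 includes permission to wait until 16+0. A loss during that permitted wait is an outcome of the strategy, not a departure from it. The objection does hold for a woman who had already refused the stitch, and the fix excepts her.

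**Conclusion.** The point holds for the per-protocol analysis. The rule in section 20, read with the 14+0 start of outcome counting and the permitted stitch window, removes a class of vaginal-arm events while keeping the same events in adherent laparoscopic-arm women. No other section corrects this. It is a stated rule rather than detail left to the SAP.

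The direction is certain for this path: it can only lower the vaginal-arm rate and so make laparoscopic cerclage look less beneficial. The size is modest. It rests on the protocol's 20% vaginal rate, 76 analysable women per arm, and assumed values of 25–75% unstitched at 14+0 with a 1–3% risk of loss before the stitch. On those values the rate falls by 0.2 to 1.8 points, and about 0 to 2 women leave. If all stitches are in place by 14+0, the bias is zero. It is worth correcting because the set serves the primary outcomes and the remedy is short, not because it threatens the main result.

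**What to change.** Add one sentence to section 20: for the per-protocol analysis, a woman allocated to vaginal cerclage whose pregnancy ends between 14+0 and 16+0 before a stitch is not classed as non-adherent, unless she had already declined the stitch or had received the other procedure; she and her event stay in the vaginal group.

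Starting both arms at a 16+0 landmark would also remove the imbalance. It would, however, discard losses between 14+0 and 16+0 that section 12 counts as primary events, so the exception is preferable for this analysis.

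For the as-treated analysis, check in the SAP how women untreated at the time of loss are handled. If groups follow the cerclage received, the same problem needs an answer there.

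Sections 11.2 and 20 should also be reconciled. The first runs the stitch window to 16+0 and the second requires a stitch earlier than 16+0, so the status of one placed on 16+0 itself is unclear.

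Cost: one sentence. Gestational age at cerclage placement and at birth or late miscarriage is already collected (sections 18 and 12). The small extra burden is recording why no stitch was placed in these few women, which is not among the variables listed in section 18.

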 - Time frame: From time of randomisation to 42 days after delivery
- Maternal morbidity surgery related.
 - Definition: Admission to ICU or a unit that provides 24-h medical supervision and can provide mechanical ventilation or continuous vasoactive drug support within 30 days of the cerclage procedure.
 - Time frame: 30 days after cerclage procedure
- Maternal morbidity pregnancy related.
 - Definition: Admission to ICU or a unit that provides 24-h medical supervision and can provide mechanical ventilation or continuous vasoactive drug support at any point during pregnancy through 42 days postpartum for pregnancy or childbirth related complications[20]
 - Time frame: From time of randomisation to 42 days after delivery
- Harm to participant surgery related.
 - Definition:
 - Damage to internal organs (yes/no)

- Need for re-operation (yes/no)
- Thromboembolic events (defined as deep vein thrombosis, pulmonary embolism or stroke) (yes/no)
- Maternal cardiopulmonary arrest (yes/no)
- Time frame: 30 days after cerclage procedure.
- Harm to participant
 - Definition:
 - Damage to internal organs (yes/no)
 - Need for re-operation (yes/no)
 - Thromboembolic events (defined as deep vein thrombosis, pulmonary embolism or stroke) (yes/no)
 - Maternal cardiopulmonary arrest (yes/no)
 - o Time frame: From time of randomisation to 42 days after delivery
- Bleeding surgery related.
 - Definition: Blood loss >500 milliliters
 - Time frame: 30 days after cerclage procedure
- Bleeding pregnancy related.
 - Definition_ Blood loss > 1000 milliliters
 - o Time frame: From time of cerclage procedure to 42 days after delivery
- Maternal infection[9] surgery related.
 - o Definition: Infection leading to antibiotic treatment
 - Time frame: 30 days after cerclage procedure
- Maternal infection[9] pregnancy related.
 - o Definition: Infection leading to antibiotic treatment
 - Time frame: From time of cerclage procedure to 42 days after delivery
- Maternal serious infection[9] surgery related.
 - o Definition: Infection leading to ICU admission
 - Time frame: 30 days after cerclage procedure
- Maternal serious infection[9] pregnancy related.
 - Definition: Infection leading to ICU admission
 - Time frame: From time of cerclage procedure to 42 days after delivery
- Preterm prelabour rupture of membranes[9]
 - Rupture of membranes before 37 weeks of gestation
 - o Time frame: At birth
- Threatened preterm labour
 - \circ $\;$ Definition: Leading to admission and intervention.

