Further, the NORACT board reserves the right to make smaller, necessary alterations in other logistic or practical aspects of running the trial for the remaining inclusion period.

In case of significant protocol amendments being added to the original protocol, a new version number will be assigned to the protocol. Simultaneously, we will add the amendments to the clinicaltrials.gov registration, and we will submit a supplementary protocol to the Central Denmark Region Committee on Health Research Ethics.

13. Harms and benefits

General considerations

The inherent risks of complications from carrying a child and giving birth exist regardless of the conduct of this trial.

The participants are women who are considered moderate to high risk of late miscarriage or very PTB and would to a large extend be offered one of the two types of interventions regardless of the trial.

Potential harms

The laparoscopic procedure is performed in general anesthesia, the intervention is a permanent placement of a foreign suture material, and the woman can only deliver from a cesarean section. Further, since the operation is performed prior to or in very early pregnancy, there is a risk of the procedure being futile or that the band needs removal (with the operative risks associated herewith) if the woman miscarries at a gestational above 14 weeks or never conceives. There is a small risk of bleeding, harm to adjacent organs and infection.

The vaginal procedure needs to be performed in each pregnancy but otherwise has limited harms. It may prevent PTB to a lower extend in selected groups of women. There is a small risk of pain, bleeding and infection.

Potential benefits

The laparoscopic cerclage may to a higher extend prevent PTB in selected groups of women. The vaginal cerclage is rarely futile as the operation is performed during pregnancy, it is performed in regional anesthesia, and it is removed by a relatively simple procedure close to term to allow for vaginal delivery.

Potential disadvantages

There may be some geographical inconveniences for the women randomized to the laparoscopic cerclage group, as they may have to travel to a laparoscopic site to have the operation performed. The risk of complications from the two procedures is no different from when the procedures are carried out in the normal clinical handling of the patients but differs slightly as described below.

Adverse event definitions

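### Surgical harms are compared only by randomised arm; the as-treated analysis stops at the primary outcomes, so no harm comparison by procedure received is planned

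*Protocol*

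**What the plan says.** Section 21 sets the basis for every outcome: "All primary analyses (primary and secondary outcomes) will be conducted on a modified intention-totreat basis". That set holds only women who carry a pregnancy beyond 14+0 weeks. On grouping it says "Participants will be analysed in the intervention group to which they were randomised", and adds that "all participants shall be included whether or not they received the allocated intervention". The one departure from allocation is then restricted: "A secondary per protocol and as-treated analysis will be performed for each treatment group for the primary outcomes only".

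Section 12 lists six surgery-related maternal outcomes among the secondary outcomes: death, intensive-care admission, harm, bleeding, infection and serious infection. The harm outcome, "Harm to participant surgery related", covers organ damage, re-operation, thromboembolism and cardiopulmonary arrest. Its window is typical of the six: "Time frame: 30 days after cerclage procedure". The clock starts at the operation, not at randomisation.

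Section 13 gives no harm rates. For laparoscopy it says "There is a small risk of bleeding, harm to adjacent organs and infection". Section 18 records the type and timing of the procedure and the blood loss. No section defines a safety population or a comparison of harms by procedure received.

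**The concern.** These six outcomes describe what follows a particular operation, yet the only planned comparison sorts women by the operation they were assigned. The design leaves room for the two to differ. Under section 20, adherence means laparoscopy before 10+0 weeks or a vaginal cerclage before 16+0 weeks, so a laparoscopic-arm woman who conceives early can pass the first limit and still receive a vaginal stitch. The trial is open-label, some sites offer only vaginal cerclage, women may have to travel for laparoscopy, and non-adherence is one of the pilot's own questions.

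The background section says evidence is limited on how to weigh each procedure's effectiveness against its disadvantages, and sections 6 and 13 present the surgical burden as a main drawback of the abdominal route. A reader of the results will want to know how often each operation causes harm. A table by allocation does not answer that once there is crossover. The restriction to the primary outcomes is explicit, so it is a choice the protocol fixes. An analysis plan that added as-treated harms would depart from it.

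**Working it through.** **The plan's own figure.** Section 15 assumes 20% versus 5%, alpha 0.05 and 80% power; section 21 uses two-sided intervals. The usual two-proportion formula without continuity correction gives 76 per arm. Inflating twice by 10% gives 76 / (0.9 × 0.9) = 93.8, so 94 per arm and 188 in total, as stated. About 76 women per arm are therefore expected in the harm comparison.

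**Dilution formula.** Let pL and pV be the 30-day risks after laparoscopic and vaginal surgery. Let cL be the share of the laparoscopic arm that receives a vaginal cerclage, and cV the share of the vaginal arm that receives laparoscopy. If risk depends only on the procedure received:

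- laparoscopic arm: (1 − cL) × pL + cL × pV
- vaginal arm: (1 − cV) × pV + cV × pL
- difference by allocation: (pL − pV) × (1 − cL − cV)

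**Assumed inputs.** The protocol gives neither harm nor crossover rates, so all of these are assumptions.

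Case A, 6% versus 3% (true difference 3.0 points):

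- total crossover 10%: 3.0 × 0.90 = 2.70 points
- 20%: 3.0 × 0.80 = 2.40 points
- 25%: 3.0 × 0.75 = 2.25 points

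Case B, 5% versus 1% (true difference 4.0 points):

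- 5% in each arm: 4.8% versus 1.2%, difference 3.6
- 10% in each arm: 4.6% versus 1.4%, difference 3.2
- 20% in each arm: 4.2% versus 1.8%, difference 2.4

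**Against sampling error.** In case A the 95% half-width is 1.96 × √[(0.06 × 0.94 + 0.03 × 0.97) / 76] = 1.96 × 0.0335 = about 6.6 points. The dilution is 0.30 to 0.75 points, so the half-width is roughly 9 to 22 times larger. In events, the dilution is 76 × 0.003 = 0.2 to 76 × 0.0075 = 0.6. In case B the half-width is 1.96 × √[(0.05 × 0.95 + 0.01 × 0.99) / 76] = about 5.4 points, against a dilution of 0.4 to 1.6 points.

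**Laparoscopic harms counted in the vaginal arm.** If 10% of 76 vaginal-arm women have laparoscopy, the expected number is 76 × 0.10 × pL: 0.2, 0.4 or 0.8 events at assumed risks of 3%, 5% or 10%. The vaginal procedure's own expected count at an assumed 1% is 76 × 0.01 = 0.76.

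**Women who have no procedure.** Their surgical risk is zero, not the other procedure's risk, so the factor above does not apply to them.

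**Women outside the analysis set.** Section 15 allows 10% for no pregnancy or early miscarriage: 94 × 0.10 = about 9 women per arm. Laparoscopy is timed before pregnancy, so many of these women in the laparoscopic arm could have been operated on. Their harms would leave the comparison.

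**The case against.** The strongest reply is that nothing here is an error. Comparison by allocation is protected by randomisation and answers the policy question; an as-treated table is not so protected. The secondary outcomes are declared exploratory, and any distortion is lost in the sampling error shown above. All of that stands, and it makes this a modest improvement rather than a flaw in the trial's main inference.

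Section 18 also says that procedure characteristics will be used in analysing outcomes, and a separate analysis plan exists that is not available here. But section 18 names no comparison of harms by procedure, and the limit in section 21 points the other way. Adverse event reporting does not fill the gap either. Serious events are reviewed case by case, but section 13 does not count admissions or attendances for common cerclage complications, such as infection and bleeding, as adverse events.

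Three stronger readings may tempt a reader.

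- *One misplaced organ injury reverses the comparison.* At 6% versus 3% the expected counts are 76 × 0.06 = 4.6 and 76 × 0.03 = 2.3; moving one event gives about 3.6 versus 3.3, with no reversal. Only a very rare component could flip, for instance 2 versus 1 by procedure becoming 1 versus 2 by allocation.
- *A woman without a procedure is wrongly counted as event-free.* She truly has no surgical complication. Section 12 also has mortality, pregnancy-related intensive-care admission and a general harm outcome running from randomisation, on which she can have events.
- *The plan makes laparoscopy look safer.* That holds only if laparoscopy is the more harmful operation and crossover occurs. The protocol quantifies neither.

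**Conclusion.** The point holds as a gap in what is planned. The 30-day surgical outcomes are analysed only by randomised arm in women who pass 14+0 weeks, and section 21 expressly keeps the as-treated analysis away from them. Crossover would shrink a true difference in procedural harm by (1 minus total crossover), provided risk depends only on the procedure received and crossovers actually receive the other procedure. The size cannot be derived from the protocol. Under the assumed rates the loss is 0.3 to 1.6 points, well below the interval half-widths of 5.4 to 6.6 points. The case for a change rests on reporting procedural harm under the procedure that preceded it, at little cost. It does not rest on a demonstrated bias of important size, and the by-allocation analysis should not be called invalid.

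**What to change.** In section 21, reword the limit on the as-treated analysis so that it covers *the primary outcomes and the surgery-related maternal outcomes*. For the surgery-related outcomes, add that:

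- every randomised woman who had a cerclage procedure is included, whether or not she later carried a pregnancy beyond 14+0 weeks;
- women are grouped by procedure received, with day 0 at that procedure;
- for a woman with more than one procedure, each 30-day window is counted under the procedure that started it (section 20 foresees a later exam-indicated vaginal cerclage in either arm);
- women with no procedure are shown separately;
- the by-allocation table is kept, and the as-treated table is labelled supportive because it is not protected by randomisation.

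The cost is a few sentences and one table. Section 18 already collects procedure type and timing, and the sample size stays at 188. Harm data must also be complete for operated women who do not reach 14+0 weeks. The one drawback is confounding in a non-randomised comparison, which the label addresses.
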